15.1. Sample Size

A total sample size of 279 evaluable subjects in US and Europe (93 per treatment group: SEP-4199 200 mg/day, SEP-4199 400 mg/day, and placebo) with a global 2-sided alpha of 0.05 will provide about 90% power to reject at least 1 truly significant comparison and about 75% power to reject both truly significant comparisons using the truncated Hochberg ($\gamma = 0.9$) procedure, assuming treatment effect sizes of 0.44 for both doses of SEP-4199. The effect sizes were selected considering the data from the completed lurasidone bipolar depression study ([Loebel 2014](#)). This effect size corresponds to a treatment difference of -3.85 for a SEP-4199 dose with a common standard deviation of 8.745 on the MADRS scale change from baseline at Week 6. An upward adjustment of approximately 5% is used to compensate for information lost due to subjects who are randomized and do not provide any postbaseline primary efficacy data. The total sample size will be approximately 294 randomized subjects (or $N = 98$ subjects per treatment group).

For the secondary efficacy endpoint, assuming the 93 subjects per treatment arm, the study will have 71% power to reject at least one truly significant comparison within the CGI-BP-S family using the regular Hochberg procedure, given a treatment difference of -0.47 for a SEP-4199 dose with a common standard deviation of 1.24 on the CGI-BP-S change from baseline at Week 6. The correlation between the primary and the secondary endpoint is assumed to be 0.8 for each treatment arm.

The sample size was calculated using the Mediana package version 1.05 within R version 3.4.2 ([R Core Team 2017](#)).

The sample size for the Japanese cohort (45 total [$N = 15$ subjects per group], including 9 dropouts) provides more than 80% probability to have a treatment difference point estimate greater than zero for the MADRS.

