15.3.5.1.1. Sensitivity Analyses

To address early dropouts under the assumption of missing not at random (MNAR), a pattern-mixture model (PMM) using a placebo-based multiple imputation method and a pattern mixture model using multiple imputations with penalties (ie, tipping point analysis by deflating the individually estimated treatment effect size by known factors) will be performed as sensitivity analyses to explore the robustness of the MMRM results for the primary analysis based on the ITT population.

MADRS total score change from baseline values over time for dropouts and for completers will be plotted by visit dropout and reason for discontinuation categorizations to assess the impact of dropouts on the efficacy endpoints. Subjects will be grouped by the visit at which they had their last efficacy score measured. This will result in five categories of subject discontinuation: Week 1 dropouts, Week 2 dropouts, Week 4 dropouts, Week 6 dropouts and Completers.

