3.4. DETERMINATION OF SAMPLE SIZE

A total sample size of 279 evaluable subjects in US and Europe (93 per treatment group: SEP-4199 200 mg/day, SEP-4199 400 mg/day, and placebo) with a global 2-sided alpha of 0.05 will provide about 90% power to reject at least 1 truly significant primary comparison and about 75% power to reject both truly significant primary comparisons using the truncated Hochberg ($\gamma = 0.9$) procedure, assuming treatment effect sizes of 0.44 for both doses of SEP-4199. The effect sizes were selected considering the data from the completed Lurasidone bipolar depression monotherapy study (Loebel 2014). This effect size corresponds to a treatment difference of -3.85 for a SEP-4199 dose with a common standard deviation of 8.745 on the MADRS scale change from baseline at Week 6. An upward adjustment of approximately 5% is used to compensate for information lost due to subjects who are randomized and do not provide any postbaseline primary efficacy data. The total sample size will be approximately 294 randomized subjects (or $N = 98$ subjects per treatment group).

For the secondary efficacy endpoint, assuming the 93 subjects per treatment arm, the study will have 71% power to reject at least one truly significant comparison within the CGI-BP-S family using the regular Hochberg procedure, given a treatment difference of -0.47 for a SEP-4199 dose with a common standard deviation of 1.24 on the CGI-BP-S change from baseline at Week 6. The correlation between the primary and the secondary endpoint is assumed to be 0.8 for each treatment arm.

The sample size was calculated using the Mediana package version 1.05 within R version 3.4.2 ([R Core Team 2017](#))

See [APPENDIX 4](#) for additional power and Type I error rate calculations.

The sample size for the Japanese cohort (45 total [$N = 15$ subjects per group], including 9 dropouts) provides more than 80% probability to have a treatment difference point estimate greater than zero for the MADRS.

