3.7. CHANGES TO ANALYSIS FROM PROTOCOL

The following changes to analysis from protocol are conducted:

- During the BDR Meeting, it was determined that there were 3 subjects who were randomized but never received a dose and 4 more subjects who were randomized, received a dose, but did not have any postbaseline MADRS/CGI data. To be consistent with the previous Sunovion Central Nervous System (CNS) studies, the definition of the intention-to-treat (ITT) population was subsequently changed from "subjects who are randomized" to

Document:

Author:

Version Number:

V2.0

Version Date:

21MAY2020

Template No: CS_TP_BS016 Revision 4
Effective Date: 01Apr2016

Reference: CS_WI_BS005

“subjects who are randomized, received at least one dose of study medication, and have a baseline and at least one post-baseline efficacy measurement in MADRS Total Score or CGI-BP-S Depression Score”.

- During the dry run 2 draft output review, some baseline characteristic tables (exposure, compliance, psychiatric and medical history) were decided to be only created for the Safety Population as the difference of subjects between the ITT and Safety populations does not affect the interpretation of the results.
- MedDRA dictionary version 19.1 was used for AE, MH and psychiatric disorders coding instead of version 20.1 (or higher) as indicated in protocol.
- WHO-DD dictionary version 01MAR2017 was used for medications coding instead of version 01SEP2017 (or more recent) as indicated in protocol.
- It was stated in the protocol that the methodology and results of the population pharmacokinetic/pharmacodynamic analyses and the relationship between SEP-4199 PK and plasma prolactin were to be described in a separate document from this SAP and reported as an appendix to the CSR. The analyses will be reported separately from the CSR.
- ECG markedly abnormal criteria Categories were updated in SAP to be more inclusive than in protocol by changing ‘>’ to ‘≥’.

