6.3. DERIVED TIME POINTS

As per protocol, Visit 6 can be an End of Treatment (EOT) visit or an Early Termination (ET) visit. If a subject terminates early, his/her ET visit will be mapped to the next planned assessment visit if it is within the window of the next planned assessment visit. This applies to both efficacy and safety data. If assessments from an ET visit cannot be mapped to the next planned assessment visit, these assessments will be excluded from any mixed model for repeated measures (MMRM) or analysis of covariance (ANCOVA) analysis. No follow-up visit data will be included in any MMRM/ANCOVA analyses. In the case of the ET being out of window of the next planned visit, it will be mapped to an unscheduled visit as appropriate.

All applicable by-visit efficacy and safety tables will include descriptive statistics for the Follow-up visit and the "Last observation visit". The "Last observation visit" is defined as the post-baseline visit at which the last non-missing observation is collected for a subject for a given parameter, including unscheduled visits or unmapped ET visits. The "Last observation visit" will be excluded from any MMRM/ANCOVA analyses.

For remapping of the ET visits, see Table 1 below.

Table 1: Mapping of the ET visit.

Parameter	Early Termination Day Criteria	Week	Analysis Visit
ECG, Vital Sign, YMRS, C-SSRS, Concomitant Medication, Last dose of Benzodiazepines/ Sedatives/Hypnotics	1 ≤ study day ≤ 9	1	Visit 3/Week 1
	10 ≤ study day ≤ 16	2	Visit 4/ Week 2
	17 ≤ study day ≤ 30	4	Visit 5/Week 4
	31 ≤ study day ≤ 44	6	Visit 6/Week 6
MADRS, CGI-BP-S, HAM-A, QIDS-SR16, AIMS, BARS, SAS	1 ≤ study day ≤ 9	1	Visit 3/Week 1
	10 ≤ study day ≤ 16	2	Visit 4/Week 2
	17 ≤ study day ≤ 30	4	Visit 5/Week 4
	31 ≤ study day ≤ 44	6	Visit 6/Week 6
SDS, EQ-5D-5L, Weight, BMI, Waist Circumference, PWC, HbA1C, Lipid panel, Serum Insulin, HOMA-IR, CRP	1 ≤ study day ≤ 44	6	Visit 6/Week 6

Document:

Author:

Version Number:

V2.0

Version Date:

21MAY2020

Template No: CS_TP_BS016 Revision 4
 Effective Date: 01Apr2016

Reference: CS_WI_BS005

Hematology, Serum Chemistry*, Urinalysis, Serum Prolactin, PK, Plasma Prolactin	1 ≤ study day ≤ 16	2	Visit 4/Week 2
	17 ≤ study day ≤ 44	6	Visit 6/Week 6

* Except for parameters listed above such as HbA1C, Lipid panel, Serum Insulin, HOMA-IR, CRP.

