Table 8 and Table 9 below show the power calculations based on 93 subjects/group sample size for a range of gamma, γ , parameters for scenario 1 and scenario 2, respectively based on 10,000 simulation runs with a 1-sided 0.025 alpha level. The larger the value of γ , the higher the power of the Family 1 test and the lower the power of the Family 2 test. In the extreme case, when the truncation parameter is set to 1, the power of the Family 1 test will be maximized (the hypotheses in Family 1 would be tested using the regular Hochberg test) and the power of the Family 2 test would be minimized (it would be reduced to 0 and it would be impossible to reject any hypotheses in Family 2 unless all hypotheses in Family 1 are rejected). On the other hand, if the truncation parameter is set to 0, the power of the Family 1 test would be minimized (the truncated Hochberg test would be reduced to the Bonferroni test) but the power of the Family 2 test would be maximized.

Table 8. Power simulations for Scenario 1

Gamma	Defn 1	Defn 2	Defn 3	Defn 4	Defn 5	Defn 6	Defn 7	Defn 8	Defn 9	Defn 10
0	0.8939	0.7645	0.8939	0.6538	0.5221	0.5221	0.7645	0.6048	0.6409	0.6457
0.1	0.8939	0.7606	0.8939	0.6677	0.5296	0.5296	0.7606	0.6164	0.6434	0.6468
0.2	0.8942	0.7578	0.8942	0.6816	0.5357	0.5357	0.7578	0.6274	0.6448	0.6487
0.3	0.8950	0.7549	0.8950	0.6939	0.5415	0.5415	0.7549	0.6370	0.6456	0.6508
0.4	0.8964	0.7513	0.8964	0.7041	0.5453	0.5453	0.7513	0.6443	0.6466	0.6500
0.5	0.8980	0.7469	0.8980	0.7152	0.5492	0.5492	0.7469	0.6518	0.6452	0.6509
0.6	0.8992	0.7411	0.8992	0.7247	0.5526	0.5526	0.7411	0.6585	0.6441	0.6496
0.7	0.9004	0.7338	0.9004	0.7341	0.5559	0.5559	0.7338	0.6652	0.6424	0.6473
0.8	0.9016	0.7265	0.9016	0.7426	0.5592	0.5592	0.7265	0.6713	0.6402	0.6455
0.9	0.9027	0.7173	0.9027	0.7517	0.5633	0.5633	0.7173	0.6782	0.6391	0.6415
1	0.9034	0.6847	0.9034	0.7605	0.5663	0.5663	0.6847	0.6847	0.6236	0.6274

The following definitions are the same by definition: defn1=defn 3, Defn2=defn7, Defn5=defn6.

Table 9. Power simulations for Scenario 2

Gamma	Defn 1	Defn 2	Defn 3	Defn 4	Defn 5	Defn 6	Defn 7	Defn 8	Defn 9	Defn 10
0	0.7856	0.6124	0.7856	0.2143	0.1445	0.1445	0.6124	0.1962	0.6002	0.1567
0.1	0.7859	0.6029	0.7859	0.2273	0.1502	0.1502	0.6029	0.2061	0.5912	0.1619
0.2	0.7858	0.5892	0.7858	0.2344	0.1536	0.1536	0.5892	0.2118	0.5780	0.1648
0.3	0.7863	0.5810	0.7863	0.2476	0.1581	0.1581	0.5810	0.2226	0.5706	0.1685
0.4	0.7868	0.5687	0.7868	0.2554	0.1604	0.1604	0.5687	0.2280	0.5586	0.1686

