APPENDIX 6. BLINDED DATA REVIEW (BDR) PROCESS

The blinded review of the SEP3800-201 data will be conducted prior to unblinding in order to permit the checking and assessment of data for the purposes of identifying additional information for analyses specified in the SAP. This process will be completed prior to unblinding.

This review will be performed by appropriate personnel including, but not limited to a biostatistician and an MD. Relevant outputs will be generated by IQVIA shortly before/after database soft lock in order to facilitate the blinded review process.

Any changes to the planned analysis based on a blinded review of data will be documented with detailed explanation for deviations from the pre-defined plans. Decisions made at this meeting will be documented prior to unblinding to be incorporated into the analysis.

The BDR process will include review of analysis populations, checking distribution assumptions, identifying any outliers, defining possible transformations for the efficacy analyses, checking stratification, and reviewing the extent of missing data for the primary and the secondary efficacy endpoints. In addition, the IPD review process detailed in [APPENDIX 7](#) will help identify any IPDs.

Document:

Author:

Version Number:

V2.0

Version Date:

21MAY2020

Template No: CS_TP_BS016 Revision 4
Effective Date: 01Apr2016

Reference: CS_WI_BS005

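### Does the sample size leave out dropout after the first post-baseline visit, so that the stated 90% / 75% / 71% power is too high?

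*Protocol*

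**What the plan says.** Protocol 15.1, repeated in the synopsis and SAP 3.4, assumes an effect size of 0.44 on MADRS for both doses (a difference of 3.85 points with SD 8.745). With 279 evaluable subjects, 93 per arm, the trial "will provide about 90% power to reject at least 1 truly significant comparison and about 75% power to reject both truly significant comparisons". For CGI-BP-S (difference 0.47, SD 1.24, correlation 0.8 with the primary endpoint) SAP 3.4 says: "For the secondary efficacy endpoint, assuming the 93 subjects per treatment arm, the study will have 71% power". SAP Appendix 4 confirms that Tables 8 and 9 "show the power calculations based on 93 subjects/group sample size".

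Protocol 15.1 gives the only US/Europe inflation: "An upward adjustment of approximately 5% is used to compensate for information lost due to subjects who are randomized and do not provide any postbaseline". It is thus for subjects with nothing on the primary endpoint after baseline. Elsewhere the plan plainly expects later losses. Protocol 15.3.5.1.1 groups subjects by their last efficacy score: "This will result in five categories of subject discontinuation: Week 1 dropouts, Week 2 dropouts, Week 4 dropouts, Week 6 dropouts and Completers". Protocol 13.1 says that subjects who leave are not replaced and that they undergo the Visit 6 assessments on leaving. SAP 6.3 then uses those assessments: "If a subject terminates early, his/her ET visit will be mapped to the next planned assessment visit if it is within the window". By its Table 1, a MADRS or CGI-BP-S score taken at early termination on Days 31 to 44 counts as Week 6.

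**The concern.** The endpoint is the change at Week 6, but the 5% allowance is used up by subjects who contribute nothing at all. A subject who gives a Week 1 score and then leaves is evaluable, yet carries less than full information about Week 6. SAP Appendix 4 lists no dropout rate, visit pattern or within-subject correlation. The one dropout count in the sample size section, 9 of 45, is for the descriptive Japanese cohort.

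If the later losses were large, the quoted power would be too high. The both-dose and CGI-BP-S figures would suffer most, and those are the ones a reader would turn to when only one dose succeeds or the secondary endpoint misses.

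**Working it through.** **1. Reproduce the plan's figures.** The inputs are those of Protocol 15.1 and SAP Appendix 4: 93 per arm, shared placebo, one-sided alpha 0.025, truncation parameter 0.9.

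- Effect sizes: 3.85 / 8.745 = 0.440; 0.47 / 1.24 = 0.379 (0.38 in SAP Table 6).
- MADRS: reject both doses if the larger p is at most (0.9 + 0.1/2) × 0.025 = 0.02375. Otherwise reject the dose with the smaller p if that p is at most 0.025/2 = 0.0125.
- CGI-BP-S: regular Hochberg at 0.025 if both MADRS hypotheses were rejected. If only one was, test the matching dose at 0.05 × 0.025 = 0.00125.

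Simulation (600,000 runs, t-tests, full Week 6 data) gives 90.2% / 74.5% / 71.1%. SAP Table 8 has 90.3% / 75.2% / 71.7%. The stated figures are right for 93 full Week 6 observations per arm.

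**2. Check the inflation.** 93 / 0.95 = 97.9, so 98 per arm. That leaves 98 − 93 = 5 per arm for subjects with no post-baseline data and nothing explicit for later dropout.

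**3. What later dropout costs under the planned analysis.** The documents give no US/Europe rate, so the rates here are assumptions: total dropout of 10% or 20% of the 98, with departures after the first score spread evenly over Days 1 to 42. Early-termination visits are attended and mapped by SAP Table 1. Of the late leavers, 9/42 then supply Week 1 only, 7/42 supply data to Week 2, 14/42 to Week 4 and 12/42 to Week 6. Effective n is the inverse of the Week 6 variance (in units of the SD squared) from the generalized least squares information for Weeks 1, 2, 4 and 6. Visit correlations are assumed: 0.5 to 0.8 constant, or decaying with 0.7 to 0.8 between Weeks 4 and 6.

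| Total dropout | No post-baseline data, per arm | Effective n per arm |
|---|---|---|
| 10% | 5 | 91–92 |
| 10% | 7/3 = 2.3 | 92–94 |
| 20% | 5 | 86–90 |
| 20% | 7/3 = 2.3 | 87–92 |

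The 7/3 rows use SAP 3.7, which reports "3 subjects who were randomized but never received a dose and 4 more subjects who were randomized" and dosed but had no post-baseline MADRS or CGI data: 7 in all. The cohort is not stated. If all were in US/Europe, that is 7 / 294 = 2.4%, against the 5 / 98 = 5.1% allowed. The unused part of the allowance covers some later dropout.

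In the second row the late leavers number 9.8 − 2.33 = 7.47 per arm. Of these, 30/42 (5.33) have no Week 6 score. So 2.33 + 5.33 = 7.67 per arm, or 23 of 294, lack one, and effective n is still 92 to 94.

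**4. Power at those sizes.**

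| Effective n | At least one dose | Both doses | CGI-BP-S |
|---|---|---|---|
| 94 | 90.5% | 75.2% | 71.8% |
| 93 | 90.2% | 74.5% | 71.1% |
| 90 | 89.2% | 72.9% | 69.3% |
| 86 | 87.7% | 70.4% | 66.7% |

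The largest fall, from 93 to 86, is 2.5 / 4.1 / 4.4 points.

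**5. The omission on the other side.** Appendix 4 has no baseline covariate either, while the primary MMRM adjusts for baseline MADRS. If 8.745 is a raw SD of change, a baseline–change correlation r reduces the variance by the factor 1 − r². The loss is cancelled when n_eff / (1 − r²) = 93, that is r = √(1 − n_eff/93). For n_eff = 86, r = √0.0753 = 0.27; for n_eff = 90, r = √0.0323 = 0.18. Such modest correlations would restore the stated power.

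**The case for a change.** The best case for acting is that the plan counts dropouts for Japan but not for the cohort that carries the power claim, and that a single clause would put this right. Harsher assumptions also give larger losses. With 20% total dropout and completers only (0.80 × 98 = 78.4 per arm), power is about 84% / 65% / 61%. With 20% of the 93 missing at Week 6 on top of the 5%, and no use of early-termination visits, effective n is 79 to 82 and power about 85–86% / 66–68% / 62–64%. The blinded data review in SAP Appendix 6 already includes "reviewing the extent of missing data for the primary and the secondary efficacy endpoints", so a pooled rate should be available.

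It stands that no US/Europe assumption about later dropout is written down, and that the basis of the two SDs is not given. The harsher figures do not describe the planned analysis: a completers-only comparison is not the MMRM, and early-termination visits are required and mapped. Rates above 20% would cost more, but neither document points to one. Rerunning the power tables with observed missingness would mix planning power with trial data and would alter no decision in an SAP finalized after that review.

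**Conclusion.** This is missing detail, not an error. The stated figures are correct for what they claim, and they are already conditional: they speak of evaluable subjects, of about 90% and 75%, and, for CGI-BP-S, of 93 per arm by assumption. Under 10% to 20% total dropout with the MMRM and the SAP 6.3 mapping, the plausible movement is 0 to 2.5 points for at least one dose, 0 to 4 for both doses and 0 to 4.5 for CGI-BP-S. This rests on assumed dropout rates, even timing, visit correlations of 0.5 to 0.8 and attended early-termination visits.

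The net direction is not settled. If 8.745 is a raw SD, baseline adjustment could cancel the loss; if it was derived from a model-based standard error in the earlier lurasidone study, dropout may already be in it; if it is baseline-adjusted and free of dropout, the loss stands. The documents do not say which. No test, alpha level, sample size or trial conclusion depends on the answer. A statistician reading the power section will take the figures as planning values given Week 6 data from 93 per arm. No change follows.

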15.2. Analysis Populations

Each population below will be created for both the US and Europe cohort and the Japanese cohort.

Intention-to-Treat Population: The intention-to-treat (ITT) population will consist of subjects who are randomized. Subjects are included in the ITT population regardless of any protocol deviations. Subjects will be analyzed according to their randomized treatment group. The ITT population is the primary population for all efficacy analyses.

Per Protocol Population: These are all ITT subjects who have no important protocol deviations that may affect the interpretation of the primary efficacy endpoint as defined in [Section 15.3.3](#). Subjects in the Per Protocol population will be analyzed according to their randomized treatment group.

Analysis of the primary and the secondary efficacy endpoints will also be performed using the Per Protocol population.

Safety Population: The safety population will consist of all subjects who randomized and receive at least one dose of study medication. Subjects will be analyzed according to the predominant treatment received. The predominant treatment is defined as the treatment to which the subject is exposed for the greatest duration during the treatment period. This will generally be the same as the randomized treatment group, unless the subject takes incorrect study medication during their entire participation in the study.

Pharmacokinetic (PK) Population: The PK population includes the Safety population subjects who have at least 1 valid postdose PK concentration value without protocol deviations or events with the potential to affect PK. The PK analysis will be based on the PK population.

15.3. Data Analysis

In general, all analyses of the Japanese cohort are descriptive in nature and will be reported separately from the US and Europe cohort, unless otherwise specified.

Descriptive summaries will be provided where appropriate for each of the endpoints. In general, summaries will be presented by treatment arm within a population.

In general, continuous outcomes will be summarized for the number of subjects, mean, 95% CI for the mean, standard deviation (SD), median, Q1, Q3, minimum and maximum. For categorical outcomes, the number and percentage of subjects will be presented.

All statistical inference analyses will be performed with 2-sided tests at a significance level of 0.05, unless otherwise specified.

In general, for analyses of change from baseline, baseline will be defined as the last non-missing measurement collected up to and including the day of first dose of study medication. Baseline data will be presented for all subjects by treatment arm.

All data from the CRFs, as well as any derived variables, will be presented in subject data listings. Unscheduled measurements will be included in the listings and will not be included in summary tables, unless specified otherwise.

SAS® software Version 9.4 or higher will be used for all analyses.

